### Prohibited Medications for SmartPill

1. No medications which may alter gastric pH around the time of the study, which includes:
  - a. Proton Pump Inhibitors for 1 week (examples: omeprazole, lansoprazole and esomeprazole, pantoprazole, rabeprazole)
  - b. Histamine2 Blockers for 3 days [(examples: cimetidine (Tagamet HB), famotidine (Pepcid), and ranitidine hydrochloride (Zantac), nizatidine (Axid)]

- c. Antacids for 1 day (examples: Maalox, Mylanta, Amphogel, Tums, Rolaids)
2. No medications that affect gastrointestinal motility for 3 full days before the start of the study and during the 5 ensuing days of study including but not limited to those drugs listed below:
  - a. Prokinetic agents, such as metoclopramide (Reglan), tegaserod (Zelnorm), domperidone (Motilium), erythromycin, zithromycin, cisapride
  - b. Anti-emetics agents, such as phenergan, compazine
  - c. Narcotic analgesic agents, such as methadone, fentanyl, percocet
  - d. Anticholinergic agents for IBS – Bentyl, Levsin
  - e. Medications for constipation, including enemas, cathartics, polyethylene glycol solutions (including Miralax), and lactulose (e.g., enulose). Patients with constipation may take medications to help stimulate a bowel movement with either milk of magnesia, 2.4 to 4.8 grams (30-60 ml), or magnesium citrate, 11 to 25 grams daily in 1 or more doses, up to 48 hours prior to SmartPill ingestion.
  - f. 5HT3 antagonists, such as Lotronex (alosetron hydrochloride) and Zofran (ondansetron hydrochloride).
  - g. Anti-diarrheal agents, such as Kaopectate (attapulgit, donnagel, rheaban), Pepto-Bismol (bismuth subsalicylate), Imodium (loperamide), and lomotil (atropine diphenoxylate).
  - h. Opiate agents used to treat diarrhea.

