### **SmartPill Capsule Ingestion Visit (Visit 2)**

This study visit should take about 2 hours to complete.

At this visit, the test procedure will be explained to the subject. They will then ingest the SmartBar, a standardized meal used to accurately measure gastric emptying time, within 10 minutes. Following ingestion, the subject will swallow the SmartPill capsule with 70cc of water. They will then receive the SmartPill receiver to carry for the duration of the study, lasting 5-7 days.

During the initial 8 hours after capsule ingestion the subject you will not be allowed to sleep because sleep may affect motility.

The subject will remain NPO for 8 hours after ingestion of the capsule. They will drink a bottle of Ensure 8 hours after ingestion. An hour after drinking the Ensure, the subject can return to their normal eating habits. Instructions will be given to the patient about completion of the daily diary in which they will document periods of ingestion, sleeping patterns and bowel movements in addition to marking it on the receiver. They will also be instructed to wait 5 minutes after each bowel movement to ensure recording of possible passage of the SmartPill.

Prior to leaving, the subject will schedule a follow up visit (visit #3) to return the receiver and the diary and discuss any questions about the study. If the patient has travelled a far distance to participate, they will be given instructions on mailing the receiver and diary back to the office.

After the visit, the subject will keep the receiver at no more than 5 feet from their body at all times during the 5-7 day period. They will be instructed to refrain from any strenuous activities during the study period. The prohibited medications will be reviewed. Additionally, they will again be asked to refrain from alcohol use for the duration of the study.

If the subject is unable to make two visits, they will be given the option to condense the first and second visit into one visit. The visit would last about 2 hours long. Prior to scheduling the condensed visit, the subject will receive an electronic copy of the consent form, in accordance with Partners Information Security guidelines, and will be notified of all medications that need to be stopped for the SmartPill. Any questions will be answered and all information about the SmartPill test will be provided.

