The first hour of the condensed visit will consist of the screening visit (visit 1). The subject will be consented by the physician prior to starting the medical history and physical, if not already previously consented during their genetics clinic visit. The subject will be given the opportunity to ask any questions they may have. The subject will also answer the questionnaires during this first hour. If eligible, the second hour of this condensed visit will consist of the SmartPill test (visit 2).

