### **Patients Travelling from Out of State**

Prior to scheduling the visit, the patient will be provided with an electronic copy of the consent form in accordance with Partners Information Security guidelines. They will be advised to read it over. The study staff will then contact the patient after a couple days and answer any questions the patient may have about the study and can be put in contact with the physician. The patient will be notified of all medications that needs to be stopped for the SmartPill and if eligible, for the sigmoidoscopy. All information for the sigmoidoscopy will be sent to the patient and the subject can be put in contact with a physician to answer any additional questions. If the patient agrees, the condensed visit will be scheduled.

The scheduled visit will be a condensed visit consisting of visit 1 and visit 2. The patient will be provided with information regarding mailing the receiver back to the study staff.

If the patient is eligible for the EMR, the visit will be condensed into 2 days. On the first day, the scheduled visit will include the screening visit (visit 1) and the sigmoidoscopy and EMR (visit 4). The patient will be consented by the physician prior to conducting the medical history and physical and completing the questionnaires. After, the patient will be prepped for the sigmoidoscopy and EMR. On the second day, the SmartPill visit will be conducted. This option will also be available for patients who are in state but cannot travel to the hospital multiple times.

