### **SmartPill Study Procedure**

Patients taking gastric acid suppressants will be instructed to stop proton pump inhibitors 1 week prior to the colonic transit study and histamine type 2 receptor antagonists 3 days prior to the colonic transit study. Patients with constipation will stop treatments for constipation at least 72 hours prior to the study and for the 5 days of the study. This includes enemas, cathartics, PEG solutions (including Miralax, enulose). Patients with constipation may take medications to help stimulate a bowel movement with either milk of magnesia, 2.4 to 4.8 grams (30-60 ml), or magnesium citrate, 11 to 25 grams daily in 1 or more doses, up to 48 hours prior to SmartPill ingestion.

All study subjects will report for the ingestion visit after an overnight fast (beginning at midnight). Date of the start of the last menstrual period for female subjects will be recorded.

The SmartPill capsule will be activated and calibrated. All study subjects will ingest a SmartBar (a nutritional bar) consisting of approximately 254 calories with 120 cc of water, followed by the SmartPill Capsule with 50 ml of water. The subject may drink an additional 50 ml of water if difficulty swallowing capsule for a total of 100 ml with capsule ingestion. Ingestion of the meal, SmartPill Capsule, and water should be completed within 10 minutes.

Intraluminal GI tract pH, pressure, temperature will be measured continuously with the SmartPill capsule. Once the capsule is ingested the patient is free to leave to the facility. At 8 hours after capsule ingestion, with the subject in a sitting position, one can of regular Ensure (Vanilla, lactose-free, 8 fluid ounces [237 ml]; 250 calories) will be ingested.

All study subjects will maintain a diary and will record times of bowel movements, meals, gastrointestinal symptoms (pain/discomfort, nausea, vomiting), and supine/sleeping times. Subjects will be instructed, if they wish, to recover and return the SmartPill capsule along with the diary and receiver at the end of the study. If they are unable to return to the office due to distance, they will be given material to send the items via FedEx.

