#### **Risks of the Washout Period**

Prior to the SmartPill initiation, patients will discontinue many of their gastrointestinal medications. During this washout period, the patient's bowel symptoms may get worse.

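### In the condensed and out-of-state paths, patients not already consented at the genetics clinic can complete the required washout only by stopping medicines before they sign consent

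*Combined protocol and SAP*

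**What the plan says.** **Washout.** Under Prohibited Medications for SmartPill, the pre-test restrictions include "Proton Pump Inhibitors for 1 week", H2 blockers for 3 days and antacids for 1 day, together with "No medications that affect gastrointestinal motility for 3 full days before the start of the study". SmartPill Study Procedure repeats two of these: patients are to "stop proton pump inhibitors 1 week prior to the colonic transit study", and the 3-day figure for H2 blockers is given there again. Risks of the Washout Period treats the stop as a study risk: "During this washout period, the patient's bowel symptoms may get worse".

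**One-visit condensed path.** This is described under SmartPill Capsule Ingestion Visit (Visit 2). Before the visit is booked, the subject is sent the consent form electronically and "will be notified of all medications that need to be stopped for the SmartPill". At the visit, "The subject will be consented by the physician prior to starting the medical history and physical"; the sentence goes on to exempt anyone who consented earlier at the genetics clinic. Screening takes the first hour and, for those found eligible, the SmartPill test takes the second.

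**Out-of-state path.** Patients Travelling from Out of State follows the same pattern: form sent, a call some days later, medicines to stop notified, and a condensed visit booked once the patient agrees. For those eligible for EMR there is a two-day version, also open to in-state patients who cannot travel repeatedly. On day 1, "The patient will be consented by the physician prior to conducting the medical history and physical and completing the questionnaires"; the SmartPill visit is on day 2. No exemption for earlier consent is written here.

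**General rules.** Study Procedures allows signing at the routine Fabry visit or before screening, and counts a patient as enrolled on signing. Subject Enrollment has a coordinator pre-screen patients who contact the study staff.

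**The concern.** A washout required only for the SmartPill test is a study procedure, and the protocol gives it its own risk paragraph. In the ordinary sequence, consent comes at or before Visit 1 and the capsule at a later Visit 2, so the washout can follow the signature. Combining the visits removes that interval, while the washout lengths stay the same.

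At stake is participant protection. Patients who are not yet enrolled, by the protocol's own definition, would carry a listed study risk with no signed consent on file. The supplied text does not say how worsening symptoms in that interval would be recorded.

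**Working it through.** The plan gives no figure for this interval, so there is none to reproduce. The check is timeline arithmetic.

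**Inputs**
- W, the required days off drug before ingestion (Prohibited Medications for SmartPill; the first two repeated in SmartPill Study Procedure): proton pump inhibitors 7, H2 blockers 3, motility drugs 3, antacids 1.
- G, the days from signing to ingestion. One-visit path: first hour to second hour of the same day, so G = 0. Two-day EMR path: day 1 to day 2, so G = 1.

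**Formula.** Days off drug before signing = max(0, W − G).

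| Drug class | W | One visit (G = 0) | Two-day EMR path (G = 1) |
|---|---|---|---|
| Proton pump inhibitors | 7 | 7 − 0 = 7 | 7 − 1 = 6 |
| H2 blockers | 3 | 3 − 0 = 3 | 3 − 1 = 2 |
| Motility drugs | 3 | 3 − 0 = 3 | 3 − 1 = 2 |
| Antacids | 1 | 1 − 0 = 1 | 1 − 1 = 0 |

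The motility-drug row takes the start of the study, in that restriction, to mean capsule ingestion.

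**Comparison cases**
- *Consented earlier at the genetics clinic:* 0 days, provided the washout starts after signing.
- *Separate visits:* G is the time from consent to Visit 2. The protocol does not fix it, but nothing forces it below W, so the washout can follow consent.

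**Does another provision close the gap?** The general option to sign before the screening visit would permit earlier signing. It does not require signing before the washout, and the condensed and out-of-state texts both place consent at the visit itself. The out-of-state text makes booking depend on the patient's agreement and mentions no signature. No supplied section describes verbal consent or a waiver covering the washout.

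**The case against.** The strongest reply is that these patients are neither uninformed nor unwilling. They receive the form, are told which medicines to stop and have their questions answered before booking. Out-of-state patients can also be put in touch with a physician, and they agree before a visit is scheduled. This stands: what is missing is documented consent, not information or informal agreement. A reader might infer that patients bear the risk before agreeing to anything, and the out-of-state section does not support that.

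Three other stronger readings are tempting.

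- *That the protocol directs patients to stop medicines before signing.* No sentence says so. The order is deduced from the visit timing and the washout lengths. Consent pages are not in the supplied text, nor is the Protocol Summary that Recruitment Procedures refers to, so a waiver or verbal process may exist elsewhere.
- *That patients will be washed out and then fail screening.* Formal eligibility is decided after the history and physical, so this can happen. But patients who contact the study staff are pre-screened first, and no failure rate can be derived.
- *That symptom questionnaires are answered off medicines in the condensed path and on them otherwise.* The documents give no interval between Visits 1 and 2 and do not tie the start of the washout to Visit 1. The difference is therefore possible but not shown. Earlier consent would not remove it either, because the questionnaires would stay in the first hour.

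**Conclusion.** The point holds for a defined group: patients in the condensed or out-of-state paths who take a barred medicine and have not already consented at the genetics clinic. If they follow the protocol, they stop that medicine before signing, for the path-specific times tabulated above. The largest is 7 days, for proton pump inhibitors in the one-visit path. Patients already consented at the clinic are outside it, as are antacid-only users in the two-day path.

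The conclusion rests on two assumptions: that consent is taken when the condensed and out-of-state sections say it is, and that no consent process outside the supplied text covers the washout. The share of patients affected is not stated and cannot be estimated. Condensing is offered to those who cannot make two visits, and recruitment reaches beyond the clinic through outside physicians and conferences, but neither fact gives a number.

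This is a sequencing fault in consent documentation. It should be corrected because it concerns participant protection and the remedy is small.

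**What to change.** Reconcile Prohibited Medications for SmartPill, Subject Enrollment, Study Procedures, SmartPill Capsule Ingestion Visit (Visit 2), Patients Travelling from Out of State and Risks of the Washout Period around one rule: documented consent precedes any medicine stop made for the study. One way is an IRB-approved remote consent process at the pre-visit contact that the protocol already plans. Record the consent date and the washout start date for each patient, so that the order can be verified.

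The cost is more than a change of wording. The condensed and out-of-state sections have a physician take consent, whereas the planned pre-visit call is made by study staff. Authorised personnel would have to take part in that contact, and remote documentation would need IRB approval. No extra visit is needed. The washout lengths and the list of barred medicines are not at issue and need not change for this purpose.

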### **Follow Up Visit (Visit 3)**

This study visit should take about 30-45 minutes to complete and will take place 5 to 7 days after Visit 2.

At this visit, the patient will return the SmartPill receiver and the study diary. We will discuss any questions or concerns they had about the study. If available, we will review the results of the SmartPill test. If it is unclear that the capsule has passed, based on the subject's history or on the study results, we may prescribe erythromycin as a promotility medication or obtain a KUB for verification.

If the patient cannot return the receiver in person, they will be provided with information on mailing the receiver back. Once the results have been reviewed, the patient will be contacted to provide the results of the SmartPill and confirmation of capsule exit.

If the patient is appropriate for the endoscopic mucosal resection, this will be scheduled within the following 3 weeks.

### **Sigmoidoscopy and Endoscopic Mucosal Resection (Visit 4)**

This study visit should take about 3.5 hours to complete.

This study visit consists of a sigmoidoscopy with biopsies and an endoscopic mucosal resection. When additional workup of gastrointestinal symptoms is warranted for altered bowel habits and/or abdominal pain, a subset of 15 treatment naive patients or with less than 6 months of treatment will be recruited from those who completed the SmartPill study for a sigmoidoscopy with biopsy collection and additional endoscopic mucosal resection.

The patient will fast the night prior and receive 2 enemas the morning of the procedure. The patient will present for completion of a clinically needed sigmoidoscopy with routine rectal and sigmoid biopsy collection. In addition, an endoscopic mucosal resection will be completed in the rectum. Biopsies will be sent to pathology for the following analysis.

1. Light microscopy with hematoxylin and eosin, periodic acid schiff, toluidine blue and acetylcholine staining.
2. Electron microscopy
3. Immunohistochemistry staining with anti-Gb3 monoclonal antibody.

All specimens will be examined for cellular morphology, other significant noted injury or structural abnormalities and location of deposition. The biopsies will be specifically analyzed for vascular and neuropathic changes. The specimens will be assessed for presence or absence of neuronal swelling, myelination, vascular sclerosis, intimal fibrosis and hypertrophy of the smooth muscles of the arterioles. The neurological and vascular cells will be assessed for deposition and quantification will be determined based on a degree of deposition scale used previously for renal biopsy analysis in Fabry disease (0 No deposit, +deposit present in a few cells, ++ deposits present in some cells, +++ deposits present in many cells) (Valbuena et al., 2008). Finally, results of analysis of all specimens will be compared to healthy aged-matched controls obtained from banked specimens in the pathology department. Once the analysis is completed, results will be correlated with the patient's gastrointestinal symptom presentation.

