Although the presence of gastrointestinal symptoms in Fabry's disease was first described more than 50 years ago by Van Wayjen in 1958, little remains known about the specific pathophysiology of the symptoms (Van Waygen, 1958). Few case reports have examined the histology and dysmotility affecting those with gastrointestinal symptoms with no large scale studies ever conducted. The symptoms are speculated to be caused by a combination of vasculopathy and neuropathy due to glycolipid accumulation causing ischemia leading to cellular

necrosis and also alterations in cell function resulting in a pro-inflammatory state. The effects on neurons and the nearby blood vessels, both mechanical and functional, are thought to cause dysmotility thus producing many of the gastrointestinal symptoms (Aerts et al., 2008). These pathophysiological mechanisms have been more extensively studied in other systems such as cardiac, renal and dermal, however little is confirmed in the actual gastrointestinal cell (Askari et al., 2007; Liguori et al., 2010; Simon, Frey, Gruler, & Bültmann, 1990)

Several case reports have been published examining the evaluation of patients with gastrointestinal complaints in Fabry disease. Superficial biopsies taken from the small bowel and rectum, showed normal villous architecture and normal surface epithelium under light microscopy with enlarged and vacuolated neurons and with globotriaosylceramide deposition in the neurons and nerve (Flynn et al., 1972; Friedman et al., 1984; Jack et al., 1991; O'Brien et al., 1982). The blood vessels and muscle cells of the muscularis mucosa were noted to have deposits with luxol fast blue positive material. Electron microscopy noted electron dense intralysosomal striped "zebra-like" bodies in smooth muscle and ganglion cells (Sheth et al., 1981). To our best knowledge, all the prior studies have completed analysis with only superficial biopsies, with no more than 2 patients per case series, and all have been published more than a decade ago. Furthermore, there has been no in depth quantification of gastrointestinal cellular injury or comparison to control specimens.

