#### **Secondary Aim - Histology**

A secondary goal will be examine all aspects of histological injury including neuronal such as myelin depletion and nerve swelling, vascular such as intima thickening and cellular hypertrophy, and GL-3 deposition. This will be completed by obtaining deep specimen biopsies of the mucosa and submucosa for analysis of the histopathology of the gastrointestinal tract in symptomatic patients with Fabry disease who are treatment naive or with only <6 months of treatment.

The specimens will be obtained by a clinically warranted sigmoidoscopy and will include an additional deeper endoscopic mucosal resection. Tissue analysis will include evaluation of abnormalities of cellular structure and morphology with correlation with gastrointestinal complaints for each patient and comparison against age matched non-Fabry patient tissue. The hypothesis is that patients will have abnormal findings on histology, which will correlate with the subjects symptoms and findings of on the questionnaires.

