## **Inclusion/Exclusion Criteria**

### *Inclusion Criteria:*

1. Adults ages 18- 70 years who have diagnosed Fabry disease either by enzyme testing in males or by enzyme and/or genetically confirmed mutation in females.
2. Adults with Fabry disease having any gastrointestinal complaints within the past year.
3. Endoscopic Mucosal Resection ONLY – Symptomatic subjects necessitating a sigmoidoscopy who are enzyme replacement therapy naive OR less than 6 months of treatment.

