#### **Recruitment Procedures**

Patients will be recruited via the Massachusetts General Hospital lysosomal storage disease clinic. The study will be presented to all patients with Fabry disease who have had gastrointestinal symptoms within the past year. Additionally, we will contact physicians who care for Fabry patients via email and conferences to inform them of the study. If patients indicate they are interested in the study to their provider, the patient may be contacted if the provider refers the patient to the study staff. Flyers with the research coordinator's contact information will also be given to interested patients and providers at conferences. At conferences, if interested, patients will be given the opportunity to sign a form that would allow them to be contacted by the study staff to learn more about the study. Subjects identified through RPDR will

receive a recruitment letter signed by the PI and the patient's provider (Please refer to the Protocol Summary for additional information). We expect to enroll all patients over a two-year period.

1. SmartPill study and questionnaires regarding gastrointestinal symptoms, quality of life and psychiatric comorbidities (Please see “study procedures” for additional information) will be administered to approximately 50 patients.
2. Histology section – Recruit up to 15 treatment naive patients or patients with less than 6 months of therapy who have lower GI symptoms including abdominal pain and/or bowel movement alterations for which a sigmoidoscopy would be clinically warranted. An endoscopic evaluation with mucosal resection will be performed.

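### Five structural injury features are recorded only as present or absent while deposition is graded; recording their extent too would recover much of the information lost for the symptom correlation

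*Combined protocol and SAP*

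**What the plan says.** Background and Significance describes earlier gastrointestinal biopsy reports in Fabry disease as superficial, old and limited to at most two patients per series, and adds that "there has been no in depth quantification of gastrointestinal cellular injury or comparison to control specimens".

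Secondary Aim - Histology covers neuronal injury, vascular injury and GL-3 deposition ("A secondary goal will be examine all aspects of histological injury including neuronal such as myelin depletion and nerve swelling"). Its hypothesis is that "patients will have abnormal findings on histology, which will correlate with the subjects symptoms".

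The Visit 4 section sets the scoring, in two systems:

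- Structural injury: "The specimens will be assessed for presence or absence of neuronal swelling, myelination, vascular sclerosis, intimal fibrosis". The fifth item scored this way is arteriolar smooth-muscle hypertrophy. These are five yes/no items.
- Deposition in neurological and vascular cells: "quantification will be determined based on a degree of deposition scale used previously for renal biopsy analysis in Fabry disease". This has four levels (0, +, ++, +++), worded as none, a few, some or many cells.

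The same section plans a comparison with age-matched banked controls and a correlation with symptoms. It names no test, coefficient or symptom score.

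On numbers, Recruitment Procedures says: "Recruit up to 15 treatment naive patients or patients with less than 6 months of therapy". The inclusion criteria limit this part to "Symptomatic subjects necessitating a sigmoidoscopy who are enzyme replacement therapy naive OR less than 6 months of treatment".

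**The concern.** The scoring of structural injury does not match the purpose given for it. The protocol points to missing quantification, then records five of its injury features without any count, percentage or grade. Two patients, one with a single swollen neuron and one with nearly all neurons swollen, would receive the same score.

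This matters most for the symptom correlation. Every histology patient is symptomatic and untreated or briefly treated, so the informative contrast may be how much injury is present and not whether there is any. With at most 15 patients there is little information to spare, and each of them undergoes an additional mucosal resection to provide the tissue.

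**Working it through.** **The plan's own sample size.** The Power section derives only the motility sample: 25/0.70 = 35.7 (stated as 35), then 35/0.70 = 50. This reproduces, but it has no bearing on histology. The 15 histology patients have no derivation. Biostatistical Analysis refers to 50 patients for histologic as well as motility findings. I use 15 because Recruitment Procedures and the Visit 4 section agree on it.

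**Inputs.** From the documents: n = 15 (an upper limit), five yes/no features, one four-level deposition scale. Assumed, because the documents do not give them: two-sided 5% test, true correlation 0.6 between extent of injury and a continuous symptom score, and prevalence from 50% to 90%.

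**Model.** Extent L = 0.6 S + 0.8 e, with S and e independent standard normal (0.8 = √(1 − 0.36)). A feature with prevalence p is present when L exceeds the (1 − p) normal quantile. Pearson test: t = r√[13/(1 − r²)] on 13 degrees of freedom.

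| Prevalence | Yes/no, Pearson | Yes/no, exact Mann-Whitney | Four grades, Spearman | P(at most 1 of 15 differs) |
|---|---|---|---|---|
| 50% | 47% | 42% | 53% | 0.1% |
| 70% | 41% | 36% | 58% | 3.5% |
| 80% | 34% | 29% | 58% | 17% |
| 90% | 23% | 15% | 58% | 55% |

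For comparison, power with an uncut, error-free extent is 70% (Pearson) or 62% (Spearman). Four grades give 57-63% with the Pearson test.

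**Analytic check.** Relative efficiency of yes/no against continuous is φ(z_p)²/[p(1 − p)]:

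- p = 0.5: 0.3989²/0.25 = 0.64
- p = 0.8: 0.2800²/0.16 = 0.49
- p = 0.9: 0.1755²/0.09 = 0.34

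**When a feature becomes untestable.** At p = 0.9, P(all 15 positive) = 0.9¹⁵ = 0.206 and P(exactly 14 positive) = 15 × 0.9¹⁴ × 0.1 = 0.343, together 0.549. With one patient in the minority, the smallest two-sided exact Mann-Whitney p-value is 2/15 = 0.133, so 5% cannot be reached. With two it is 2/105 = 0.019. The expected minority at 90% is 15 × 0.1 = 1.5 patients.

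**Limit set by n = 15.** For 80% power even with a continuous measure, the Fisher z approximation needs r = tanh[(1.960 + 0.842)/√12] = 0.67.

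**The case against.** Several points on the other side stand.

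- A reader might infer that all tissue injury is scored yes/no. It is not: deposition, which the histology aim counts among the aspects of injury, is graded in the very next sentence of the Visit 4 section.
- A reader might also infer that most features will be near-universal and so cannot correlate with symptoms. The documents do not support this. The Background's case reports mention enlarged, vacuolated neurons, which bear on one of the five features. They give no frequency for it and say nothing about the prevalence of the other four. At 50% to 80% prevalence the yes/no score loses power but can still show a correlation.
- Nor would the study merely repeat the case reports. It adds deeper tissue, more patients, controls and graded deposition. A high prevalence in patients could even help the control comparison if controls rarely show the feature.
- The 70% is an upper bound. Affected/total in a small specimen carries counting noise, and the documents do not say how many neurons or vessels a section will show. Assuming a probit-normal extent with 50% to 80% of cells affected on average, power was 25-49% with 5 cells per patient, 36-58% with 10 and 47-62% with 20.
- Replacing the deposition grade would gain at most about 7 points (63% to 70%), possibly nothing. That change is not proposed.

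Counting noise does not rescue yes/no scoring, because the same few cells determine whether a feature is called present. With 5 to 20 cells and about 65% affected on average (assumed), counts gave 48-61% power and an any-cell-affected score 5-15%. The advantage narrows when few cells are affected.

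**Conclusion.** The point holds for the five structural features and for those only. Their yes/no scoring falls short of the quantification gap the protocol names. Under the stated assumptions, power for the symptom correlation drops from about 70% (error-free extent) or 57-63% (four grades) to 47%, 34% and 23% at prevalences of 50%, 80% and 90%. The loss is present even at the most favourable prevalence; near-untestability arises only at about 90% or more, or by symmetry 10% or less.

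The size of the loss rests on the assumed correlation, test and prevalence; the rank-based results show the same pattern at lower levels. Better scoring does not make 15 patients adequate for firm inference. This is a cheap improvement to a secondary aim and does not invalidate the study.

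**What to change.** In the Visit 4 section:

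1. For each of the five structural features, have the same reader record affected over total neurons or vessels on the sections already planned. Where counting is impractical, use a 0 to +++ extent grade parallel to the deposition scale. State what counts as affected for each feature; for myelination, say whether the finding is depletion, as the aim implies.
2. Use that percentage or grade, one value per patient and feature, as the analysis variable for both the control comparison and the symptom correlation.
3. Keep present/absent as a descriptive summary, and leave the deposition grade as it is.
4. Label the symptom correlation in at most 15 patients as exploratory.

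The cost is some extra reading time for at most 15 patients and their controls, with no new tissue or stain. In small specimens, counting noise will keep the gain below the error-free figure; recording the denominators makes that visible.
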